2.4.3 Study Period

[figure not shown]
The cross-over study design and the treatment plan are illustrated in Figure 1. Pregabalin (or matching placebo) will be administered for four weeks in each period. The target dose will be increased from 75mg BID to 300mg BID within 7 days (per schedule in Fig. 1), and continued for an additional 22 days.

In case of any grade 2 adverse events (Common Terminology Criteria for Adverse Events – CTCAE version 4.0), the dose will be reduced to the last dose prior to dose increase (i.e. to 150mg BID from 300mg BID; to 75mg BID from 150mg BID). If the adverse effect diminishes to \leq Grade 1, one attempt to dose escalate will be allowed after 3 additional days. If the dose escalation is not tolerated (i.e. recurrent grade 2 adverse event), the treatment will be continued at the previous (lower) dose until day 28. Any CTCAE \geq grade 3 will trigger subject withdrawal from the study.

At the end of treatment sequence, the dose will be tapered over 3 days (e.g., 150mg BID for 2 days, then 75 mg BID for 1 additional day) followed by 10 days of study drug-free washout (end of week 6). In subjects with CrCL 30-60 mL/min, the target (maximum) dose will be 300mg/day. In these subjects the dose will be tapered over 3 days of 75mg BID dosing. If subject's highest tolerable maintenance dose was 75mg BID, the taper schedule will be 75mg QD over 3 days.

The subjects will return on day 28 ± 2 days [prior to washout period] for Visit 2 to turn in the 4 questionnaires which were completed on day 28 (week 4a), sensory mapping, PK blood sample and a blood sample for renal and hepatic function tests will be obtained. After the washout period (end of week 6), the subjects will return to Washington University Medical Center for Visit 3, prior to second treatment sequence. The subjects will undergo QST and CPM procedures (Fig. 1), and complete the appropriate questionnaires (SPI, NPSI, BPI, DAPOS). Thereafter, the second 4-week treatment sequence will be scheduled for weeks 7-10, according to the same titration schedule as sequence 1. Three day dose tapering-down will be practiced at the end of second treatment sequence in the same manner as was performed for the first treatment. The subjects will return for the final assessment visit [Visit 4] approximately 3 days after end of week 10 (end of 3-day taper). Safety and efficacy data, a PK blood sample and a blood sample for renal and hepatic function tests will be obtained, turn in 4 questionnaires which were completed on day 28 (week 4b), sensory mapping, and the optional skin biopsy in subjects who agreed, will be obtained at Visit 4.

Figure 1.

Legend: BPI – brief pain inventory; NPSI – neuropathic pain symptom inventory; DAPOS – depression, anxiety and positive outlook scale; SPI – sleep problem index; QST – quantitative sensory testing; CPM – conditioned pain modulation. Tx – treatment.

Rescue Analgesia

Study subjects will be allowed to take oral acetaminophen (paracetamol) as rescue analgesic at a dose of 1 gram up to 4 times/day. FDA-approved 500mg acetaminophen tablets will be purchased and provided by the investigators. If the patient has been receiving PRN short-acting opioids (with or without acetaminophen) for non-CIPN pain, up to 4 daily doses will be allowed during the study, with daily recording of analgesic consumption. The total amount of acetaminophen (from opioid-acetaminophen combination and PRN acetaminophen alone) will not exceed 4 grams/day. In subjects with liver disease (AST or ALT increased, but less than 3 times the upper normal level), the total daily dose of acetaminophen will be limited to 2 grams. Based on these considerations, each patient will receive individual written instructions regarding PRN analgesic use, and will be required to report it appropriately.

Outcomes Assessment:

Clinical Efficacy

Patients will complete an electronic diary with daily report of their average and maximum daily pain intensity, recorded every evening before bedtime. The percentage of pain reduction for primary outcome will be assessed from the difference between baseline average pain intensity and the average pain intensity of last 5 days of treatment (day 24-28), on 0-10 NRS.

Secondary efficacy outcomes will include: 1) The difference between baseline maximum pain intensity and the maximum pain intensity of the last 5 days of treatment, on 0-10 NRS; 2) The proportion of patients achieving 50% or more pain relief with pregabalin vs. placebo treatment; 3) Difference in Pain Severity and Pain Interference scales of the BPI, assessed at baseline and day 28 of treatment. The daily use of rescue analgesia (oral acetaminophen) will also be recorded.

Table 1. Data assessment schedule

Required Assessments	Screening and Enrollment Baseline Visit	Week 1a	Week 2a	Week 3a	Week 4a	End of Treatment A (Day 28 +/- 2)	Wash-out	Study crossover visit	Week 1b	Week 2b	Week 3b	Week 4b	End of Study Visit (Day 30 +/- 3)
Study visits	Visit1 (a/b)*					Visit2		Visit3					Visit 4
Informed consent	✓												
Pregnancy (urine Hbhcg) test for women	✓												
Comprehensive Metabolic Panel (CMP) blood test**	✓					✓							✓
Inclusion/exclusion criteria	✓												
Randomization	✓												
Demographic data collection	✓												
Sensory Mapping	✓					✓		✓					✓
BPI questionnaire	✓				✓			✓				✓	
NPSI questionnaire	✓				✓			✓				✓	
DAPOS questionnaire	✓				✓			✓				✓	
SPI questionnaire	✓				✓			✓				✓	
QST	✓							✓					
CPM	✓							✓					
Dispense study drug	✓							✓					
Pain intensity 0-10 NRS	✓	daily	daily	daily	daily			✓	daily	daily	daily	daily	✓
Adverse Event assessment		daily	daily	daily	daily				daily	daily	daily	daily	✓
Telephone communication		weekly	weekly	weekly	weekly				weekly	weekly	weekly	weekly	
Blinding questionnaire***		✓											
Pill count								✓					✓
Blood sample (PK)						✓							✓
Skin biopsy (optional)													✓

*Visit 1 may be conducted over 2 visits to complete all assessments if required for subject tolerability or convenience

** A blood sample for CMP will not be obtained if recent (<30 days) results are available.

*** Blinding questionnaire to be administered via EMA device on Day 5 of study drug treatment

Subject Blinding Perception

On Day 5 of the first treatment cycle, subjects will answer a brief question related to their randomization of drug vs placebo using the smartphone device.

Safety

Voluntary reporting of any adverse effects (AEs) will be recorded daily in the electronic diary. In addition, possible AEs will be addressed during weekly communications with the subjects. The

subjects will be able to contact the PI or study coordinator with regard to any AE, and moderate to severe AEs will be addressed and treated, if necessary. Any serious or unexpected AE will be promptly reported to the IRB and to the QASMC (refer to Section 3.0). All subject withdrawals from the study (for any reason) will be documented and the reasons for withdrawal carefully recorded.

Compliance

Compliance will be enhanced by weekly scheduled telephone communication with the subject by the study coordinator, and compliance assessment will be performed by pill count at the end of each study sequence. The electronic diaries have a built-in trigger reminder that will be set both for taking the study medication and for completing pain and AE assessment, according to patient preferences.

Pharmacokinetics

A single blood sample (approx. 5cc) will be collected at the end of each treatment period (approx. day 28 for each drug randomization assignment) to determine plasma level of pregabalin.

Electronic data collection

The pain intensity and AE data will be collected via a validated smart phone-based program, administered as a diary provided to each subject on a locked smart phone. This approach (Ecological Momentary Assessments, EMA) is currently in use with other Washington University in St. Louis IRB-approved protocols. The phones will be provided to subjects by the study team and run only the EMA program. The subjects will receive daily triggers for data assessment, with reminder cues until it is completed. The daily assessment will measure the average and maximum pain intensity (on 0-10 NRS), reported once a day before bedtime and will include voluntary AE report. The diary will also include daily information on the amount of rescue analgesia consumed by the patient. Data are automatically uploaded to a secure Cloud based server and transmitted to a WU firewall protected network server. Subject data will be reviewed approximately weekly by the research team. Only the research team will have access to the password for retrieval of data from the smartphone device. All data will be saved using a linked study ID number. There are no patient identifiers saved to the device.

Skin Biopsy

Subjects will be asked to undergo a 3mm skin punch biopsy in the lower leg (10 cm above the lateral malleolus) to be performed at the final study visit. This is to explore possible correlations between changes in small nerve fiber morphology and the treatment response to the study drug. The measures obtained from the skin biopsies include intraepidermal nerve fiber density (IENFD) and length density (NFLD) of PGP9.5 – stained small fibers. This skin biopsy is a standard procedure using aseptic technique, after local infiltration with lidocaine and will be performed by a trained health care professional. Refusal to undergo this procedure does not exclude subjects from participation in the research study. This procedure is voluntary.

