2.3.2 Exclusion Criteria

Subjects will not be enrolled if any of the following criteria exist:

1. Hypersensitivity to pregabalin.
2. Current treatment with pregabalin.
3. CIPN that may be associated with previous treatment with a vinca alkaloid (e.g. vincristine, vinblastine), or current treatment with a vinca alkaloid.
4. History of diabetes mellitus or a neurological disorder with any previous signs of distal symmetric polyneuropathy.
5. Moderate to severe renal failure (Clcr < 30mL/min).

6. ALT (SGPT) or AST (SGOT) > 3 times the upper limit of normal.
7. Planned surgeries or radiation treatment within 10 weeks following study inclusion.
8. Inability to complete pain self-report.
9. Pregnancy or lactation
10. Patients with seizure disorders treated with anticonvulsants
11. Current participation in a trial with another investigational agent, unless co-enrollment is approved by the PIs of both studies.
12. Concomitant medication as follows:
 - Subjects treated with gabapentin or other anticonvulsant for neuropathic pain will be required to taper the medication and discontinue for at least 2 weeks prior to study initiation.
 - Patients on antidepressant treatment for pain or depression (TCAs, SSRI, SNRIs etc. will be allowed to continue their medications provided they have been on a stable dose for at least 4 weeks before study initiation. No dose regimen changes of antidepressants will be allowed during the study period.
 - Patients on around-the clock opioid treatment (including tramadol) will be allowed to continue their medication provided they have been on a stable dose for at least 4 weeks before study initiation. The maximum allowed dose of opioid will be equivalent to 60mg oral morphine sulphate. Patients with higher doses will be required to taper down their opioid dose to maximum 60mg oral morphine equivalent, and continue on stable dose for 4 weeks before enrollment in the study. PRN short-acting opioids for painful CIPN treatment will not be allowed. Patients receiving PRN short-acting opioids (with or without acetaminophen) for pain other than CIPN will be allowed up to 4 daily doses, with daily recording of analgesic consumption.
 - Treatment with NSAIDs will be discontinued at least 2 weeks before study initiation. However, low-dose aspirin (≤ 325 mg/day) will be allowed.

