2.4.2 Pre-Study Period

At the screening visit, after obtaining signed informed consent, we will collect patient demographic data including details on cancer type and status, chemotherapy regimen(s) and cumulative doses, history of chronic pain, concomitant diseases and medication, and duration of painful CIPN. A blood sample for CMP will be obtained for determining serum creatinine concentration and liver transaminases (ALT and AST). If subject's lab tests results are available within the past 30 days, we will utilize these without the need of obtaining new renal and hepatic function tests. In addition, the patients will complete the following questionnaires: Brief Pain Inventory (BPI), Neuropathic Pain Symptom Inventory (NPSI), and Depression Anxiety and Positive Outlook Scale (DAPOS). Average and maximum daily pain intensity in the past week will be recorded as baseline pain intensity measure.

The subjects' extremities will be mapped for spontaneous pain, and response to the following sensory stimulation: cold (20°C Thermal Roller, Somedic), warm (40°C Thermal Roller, Somedic), pinprick (# 5.88 Semmes-Weinstein monofilament, 60mN target force, North Coast) and brush (SenseLab 0.5 brush, Somedic) (Finnerup, Sorensen et al. 2007). The probability of neuropathic pain will be graded as possible, probable, or definite according to Treede et al. criteria (Treede, Jensen et al. 2008). The results of sensory mapping will provide the information for the criterion on presence of any objectively tested positive or negative neurological signs in the painful territory. Photographs of the mapped extremities will be taken (in a way not to include any part of the subjects' face or other identifying information), for accurate reproduction of areas of sensory disturbance.

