2.4.10 Clinical Procedures and Laboratory Tests

Due to the risk of decreased clearance of pregabalin in participants with moderate to severe renal insufficiency, active surveillance to prevent drug accumulation will be performed. Plasma creatinine will be determined before study enrollment and only patients with a CrCl ≥ 30 [by Cockcroft-Gault formula] will be eligible. If renal insufficiency (CrCl <30 mL/min occurs, the subject will be withdrawn from the study. If CrCl 30-60 mL/min, the maximum dosage will be 300mg/day, per Lyrica® prescribing information.

Concomitant analgesic medications:

- Subjects treated with gabapentin or other anticonvulsant for neuropathic pain will be required to taper down the medication and to discontinue it at least 2 weeks prior to study initiation.
- Patients on antidepressant treatment for pain or depression (TCAs, SSRI, SNRIs etc. will be allowed to continue their medications provided they have been on a stable dose for at least 4 weeks before study initiation. No dose regimen changes of antidepressants will be allowed during the study period. Patients requiring dose regimen changes will be withdrawn from the study.
- Patients on around-the clock opioid treatment (including tramadol) will be allowed to continue their medication provided they have been on a stable dose for at least 4 weeks before study initiation. The maximum allowed dose of opioid will be equivalent to 60mg oral morphine sulphate. Patients with higher doses will be required to taper down their opioid dose to maximum 60mg oral morphine equivalent, and continue it for 4 weeks before enrollment in

the study. PRN short-acting opioids for painful CIPN treatment will not be allowed. Patients receiving PRN short-acting opioids (with or without acetaminophen) for pain other than CIPN will be allowed up to 4 daily doses, with daily recording of analgesic consumption.

- Treatment with NSAIDs will be discontinued at least 2 weeks before study initiation. However, low-dose aspirin (≤ 325 mg/day) will be allowed.

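### The Table 1 footnote extends the 30-day CMP waiver to Visit 2, against the protocol text; a lesser point is that the 2 g/day acetaminophen cap stops short of 3 x ULN

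*Combined protocol and SAP*

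**What the plan says.** **CMP waiver.** In Table 1 (section 2.4.3) the CMP row is ticked at the baseline visit, at Visit 2 and at Visit 4. The double asterisk is on the row label, and its footnote names no visit: "A blood sample for CMP will not be obtained if recent (<30 days) results are available".

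The body text is narrower. Section 2.4.2, which describes the screening visit, provides that if "lab tests results are available within the past 30 days, we will utilize these without the need of obtaining new renal and hepatic" function tests. For Visit 2, section 2.4.3 states without exception that "a blood sample for renal and hepatic function tests will be obtained", and it says the same for Visit 4.

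Section 2.4.10 uses renal function in two ways. It caps pregabalin at 300 mg/day when CrCl is 30-60 mL/min, and it adds: "If renal insufficiency (CrCl <30 mL/min occurs, the subject will be withdrawn from the study".

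**Acetaminophen.** The Rescue Analgesia paragraph of section 2.4.3 sets a general ceiling of 4 g/day from all sources. The reduced ceiling of 2 g applies as follows: "In subjects with liver disease (AST or ALT increased, but less than 3 times the upper normal level), the total daily dose of acetaminophen" is limited to that amount. The hepatic exclusion in section 2.3.2 is "ALT (SGPT) or AST (SGOT) > 3 times the upper limit of normal".

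**The concern.** The footnote and the text give site staff opposite instructions for the same blood draw. One says a sample will not be taken if a recent result exists; the other says it will be taken. Someone working from the schedule table could follow the footnote.

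Visit 3 has no CMP, yet period 2 drug is dispensed there. Visit 2 is therefore the only scheduled renal and hepatic check between screening and Visit 4, and the only scheduled on-study one before period 2 that could bring the CrCl rules of section 2.4.10 into play. If a result from around first dose stands in for it, a patient whose renal function fell during period 1 could start period 2 without a scheduled test having shown it.

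The acetaminophen rule has a smaller fault. It halves the ceiling for raised liver enzymes, but as written the lower ceiling stops just short of 3 x ULN. An on-study value slightly below that line means 2 g/day, while one at or slightly above it means 4 g/day unless another rule intervenes. That runs against the purpose of the cap.

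**Working it through.** The plan states no figure of its own on this point, so there is none to reproduce. The check is day arithmetic for the footnote and threshold logic for the cap.

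**Step 1. Inputs for the footnote (all from section 2.4.3).** Visit 2 is on day 28 ± 2, so day v = 26, 27, 28, 29 or 30. The waiver needs a result less than 30 days old. Let k be the number of days from the screening draw to first dose.

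**Step 2. Day count.** The text does not settle whether first dose is day 0 or day 1. Titration takes 7 days, "and continued for an additional 22 days", and 7 + 22 = 29 days fits days 0 to 28. Four weeks of treatment ending on day 28 fits days 1 to 28. Both counts are shown.

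**Step 3. Age of the screening CMP at Visit 2.** With first dose on day 0, age = v + k. With first dose on day 1, age = v - 1 + k.

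| k (days before first dose) | Age, day-0 count | Visit 2 days (of 5) with age < 30 | Age, day-1 count | Visit 2 days (of 5) with age < 30 |
|---|---|---|---|---|
| 0 | 26-30 | 4 | 25-29 | 5 |
| 1 | 27-31 | 3 | 26-30 | 4 |
| 2 | 28-32 | 2 | 27-31 | 3 |
| 3 | 29-33 | 1 | 28-32 | 2 |
| 4 | 30-34 | 0 | 29-33 | 1 |
| 5 | 31-35 | 0 | 30-34 | 0 |

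A screening CMP can therefore displace the Visit 2 test only if drawn 0-3 days (day-0 count) or 0-4 days (day-1 count) before first dose, and mostly on only some of the permitted days.

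**Step 4. Other results.** The footnote does not require the recent result to be a study sample. Any other available CMP under 30 days old at Visit 2 would also trigger it, whatever the value of k.

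**Step 5. Visit 4.** Table 1 puts Visit 4 at day 30 ± 3 of period 2. If period 2 starts directly after day 42 (end of week 6), Visit 4 falls between study days 42 + 27 = 69 and 42 + 33 = 75. A CMP taken at Visit 2 would then be 69 - 30 = 39 to 75 - 26 = 49 days old, never under 30. The Visit 2 study sample cannot waive the Visit 4 test; only some other recent result could.

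**Step 6. Acetaminophen thresholds.** "Increased" is not quoted here as a defined term; it is taken to mean above ULN.

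| AST or ALT | At entry | Literal daily ceiling |
|---|---|---|
| Not above ULN | eligible | 4 g |
| Above ULN, below 3 x ULN | eligible | 2 g |
| Exactly 3 x ULN | eligible | 4 g |
| Above 3 x ULN | excluded | does not arise at entry |
| At or above 3 x ULN on study, no grade 3 event | already enrolled | 4 g |

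The difference is 4 - 2 = 2 g/day. At entry it concerns a single value; on study it concerns a band whose upper end depends on how AST and ALT map to CTCAE grades, which the documents do not set out.

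**The case against.** **On the footnote.** The body text largely answers the question. Section 2.4.2 places the waiver in the screening visit, section 2.4.3 calls for the Visit 2 and Visit 4 samples without exception, and section 2.4.10 opens by promising active surveillance against drug accumulation, which a pre-dose result cannot provide. The footnote looks like shorthand for section 2.4.2. The screening window is also narrow. Section 2.4.1 requires eligibility to be confirmed before any intervention, so the result would have to be back within those 0-4 days. A patient who must first stop gabapentin or an NSAID for at least 2 weeks falls outside the window if the CMP precedes that washout. The CrCl withdrawal rule also applies however the fall is detected.

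All of this stands, and it rules out a stronger reading that a reader might infer: that the plan intends to skip the Visit 2 test. What remains is a plain conflict between table and text, in a case the arithmetic shows can occur.

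**On the cap.** The 3 x ULN bound probably just mirrors the exclusion criterion. The 4 g figure is a ceiling, and patients receive individual written instructions. Grade 2 events lead to a study drug reduction (section 2.4.3) and grade 3 or higher to withdrawal (section 3.2). Section 2.4.3 adds that "moderate to severe AEs will be addressed and treated, if necessary", and the investigator may withdraw a subject under section 3.2.

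These are real backstops, although none names acetaminophen. They defeat the tempting claim that the highest enzyme values are left uncapped, because a grade 3 event takes the patient out of the study. They do not remove the literal gap at exactly 3 x ULN, or at and above it short of grade 3.

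**Conclusion.** The point holds as a minor patient-safety correction. The main part is the table-text conflict over the CMP waiver, where the text favours the safer, screening-only reading. The lesser part is the upper bound on the 2 g/day cap.

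The size is limited. For the footnote, it is the possible loss of one scheduled test, through a screening CMP drawn within the last 3 or 4 days before first dose or through another recent result. For the cap, it is a ceiling 2 g/day higher for a narrow group. The documents do not give the number of patients affected in either case.

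The conclusion assumes that the footnote is applied as printed and, for the Visit 4 dates only, that period 2 starts directly after week 6. A reader might also infer that the cap is fixed by baseline enzymes and needs a stated recheck. The text does not tie it to baseline, so a patient at 2 x ULN at Visit 2 is already covered and no defect is shown there. Nothing here affects the primary analysis or power.

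**What to change.** 1. In the Table 1 footnote, state that the 30-day allowance applies to the screening sample only, in line with section 2.4.2.
2. In the Rescue Analgesia paragraph, apply the 2 g/day limit, from all sources, to any AST or ALT above ULN, with no upper bound.

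Both are wording changes. The cost is an occasional extra CMP and slightly less rescue analgesia for a few patients.
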